5.2 Primary Safety Endpoint (Evaluated through 30 Days post procedure) [Device Group only]

Overall rate of device and procedure related Major Adverse Events (MAEs) through 30 days post-procedure (including death, stroke, myocardial infarction, pericardial effusion requiring drainage, left circumflex coronary artery injury requiring intervention, mitral valve reintervention and access site and vascular complications requiring intervention. The primary safety endpoint was chosen to detect any concerns relating to safety of the Edwards Cardioband System implantation procedure.

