5.3 Secondary Safety Endpoints (through 30 Days) [Device Group only]

- 1. Death
- 2. Stroke
- 3. Myocardial infarction
- 4. Pericardial effusion requiring drainage
- 5. Mitral valve reintervention
- 6. Access site and vascular complications requiring intervention
- 7. Left circumflex coronary artery injury requiring intervention
- 8. Need for a new permanent pacemaker

5.4 Secondary Endpoints through 1 Year (Powered):

The following key secondary efficacy endpoints will be tested in comparison to control in a hierarchical order to preserve statistical power.

- 1. MR ≤ 1+
- 2. NYHA Class
- 3. Kansas City Cardiomyopathy Questionnaire (KCCQ)
- 4. 6 Minute Walk Test (6MWT)
- 5. SF-36v2 Health Survey (SF-36)
- 6. Heart Failure Hospitalizations
- 7. Cardiovascular mortality
- 8. All-cause mortality

5.5 Other Secondary Endpoints:

The following outcomes will be assessed for device and control, where appropriate:

For the Device Arm:

1. Device Success (measured at 30 days): Device is deployed as intended and the delivery system is successfully retrieved as intended at the time of the patient's exit from the cardiac catheterization laboratory (per device analysis).

- 2. Procedural Success (measured at 30 days): Device success with evidence of MR reduction ≤ MR2+ at discharge and without the need for a surgical or percutaneous intervention prior to hospital discharge (per patient analysis).
- 3. Clinical Success (measured at 30 days): Procedural success with evidence of MR reduction ≤ MR2+ and without MAEs* at 30 days (per patient analysis).
 - *Major adverse events (MAE) defined as death, stroke, myocardial infarction, pericardial effusion requiring drainage, left circumflex coronary artery injury requiring intervention, mitral valve reintervention and access site and vascular complications requiring intervention.
- 4. Responder analysis percentage of patients who achieve:
 - a. $MR \le 2+$, and
 - b. Meets at least two of the following criteria:
 - Improvement vs. Baseline in Symptoms (e.g., NYHA Class improvement ≥
 - Improvement vs. Baseline in Functional Status (6MWD improvement ≥ 30 ii. meters)
 - Improvement vs. baseline in QoL (KCCQ improvement ≥ 5 points) iii.

For both the Device and Control Arms:

- 1. Patient success (measured at 1 year) is defined as
 - a. Patient remains alive and stroke free, and
 - b. No re-hospitalizations (or equivalents) for HF, and
 - c. Patient meets at least two of the following criteria:

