APPENDIX B: STUDY DEFINITIONS

Endpoints identified in the Clinical Events Committee (CEC) Charter will be adjudicated by the independent Clinical Events Committee. A detailed CEC Charter will further define the endpoint definitions. In case of inconsistency between the protocol and the CEC Charter, the CEC Charter will be the final determining document.

ACCESS SITE

Any location (arterial or venous) traversed by a guide-wire, a catheter or a sheath.

ACCESS SITE AND VASCULAR COMPLICATIONS REQUIRING INTERVENTION

Complications (i.e. dissection, perforation, arteriovenous fistula, pseudoaneurysm, retroperitoneal hemorrhage, thromboembolism etc.) requiring intervention (percutaneous or surgical).

ATRIAL FIBRILLATION (AF) – Heart Rhythm Society Guidelines

Paroxysmal: Recurrent (≥ 2) atrial fibrillation episodes that terminate spontaneously within 7 days.

Persistent: Atrial fibrillation that is sustained beyond 7 days, or lasting less than 7 days but necessitating pharmacologic or electrical cardioversion.

Longstanding Persistent AF: Continuous atrial fibrillation of greater than 1 year duration.

Permanent: Atrial fibrillation in which cardioversion has failed or not been attempted.

BLEEDING (MVARC)

Minor

Any overt, actionable sign of hemorrhage (e.g., more bleeding than would be expected for a clinical circumstance, including bleeding found by imaging alone) that meets ≥ 1 of the following: requiring nonsurgical medical intervention by a health care professional; leading to hospitalization or increased level of care; prompting evaluation; or requires 1 or 2 units of whole blood or packed red blood cell (RBC) transfusion and otherwise does not meet criteria for major, extensive, or life threatening.

Major bleeding

PROTOCOL NUMBER: 2017-05

Overt bleeding either associated with a drop in the hemoglobin level of \geq 3.0 g/dl or requiring transfusion of ≥3 units of whole blood or packed RBC AND does not meet the criteria of life-threatening or extensive bleeding.

Extensive

Overt source of bleeding with drop in hemoglobin of ≥ 4 g/dl or whole blood or packed RBC transfusion

Life-threatening

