Major pericardial effusion requiring drainage, also known as cardiac tamponade (CT) is a life-threatening, slow or rapid compression of the heart due to the pericardial accumulation of fluid, pus, blood, clots or gas as a result of inflammation, trauma, rupture of the heart, aortic dissection or iatrogenic causes (invasive procedure-related). Cardiac tamponade meets the MVARC definition for device-related technical failure issues and complications and the MVARC definition for life threatening bleeding in a critical organ.

PROTOCOL NUMBER: 2017-05

REINTERVENTION

Any intervention on the previously implanted study device (repair, alteration or replacement)

STROKE and TIA

Acute episode of a focal or global neurological deficit with at least one of the following: change in level of consciousness, hemiplegia, hemiparesis, numbness or sensory loss affecting one side of the body, dysphasia or aphasia, hemianopia, amaurosis fugax, or other neurological signs or symptoms consistent with stroke.

Cases will be categorized as either

- 1) Stroke Duration of a focal or global neurological deficit ≥24 hours; OR <24 hours, if available neuroimaging documents a new hemorrhage or infarct; OR the neurological deficit results in death
- 2) TIA Duration of a focal or global neurological deficit <24 hours, any variable neuroimaging does not demonstrate a new hemorrhage or infarct

Stroke classification

Ischemic – An acute episode of focal cerebral, spinal, or retinal dysfunction caused by infarction of central nervous system tissue

Hemorrhagic – An acute episode of focal or global cerebral or spinal dysfunction caused by intraparenchymal, intraventricular, or subarachnoid hemorrhage

A stroke may be classified as undetermined if there is insufficient information to allow categorization as ischemic or hemorrhagic

Stroke definitions

Disabling stroke – a mRS score of 2 or more at 90 days and an increase of at least one mRS category from an individual's pre-stroke baseline

Non-disabling stroke – a mRS score of less than 2 at 90 days or one that does not result in an increase of at least one mRS category from an individual's pre-stroke baseline

Patients with non-focal global encephalopathy will not be reported as a stroke without unequivocal evidence of cerebral infarction based upon neuroimaging studies (CT scan or Brain MRI).

RENAL COMPLICATIONS (Long-Term)

Long-term Renal Complication is defined as onset of renal replacement therapy

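### The closing rule of the stroke definition accepts only infarction as imaging proof for non-focal global encephalopathy, which conflicts with the protocol's own hemorrhagic stroke definition and could leave a proven hemorrhage out of the stroke count

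*Protocol*

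**What the plan says.** All the relevant stroke wording is in Protocol Appendix B, under Stroke and TIA.

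- **Entry:** "Acute episode of a focal or global neurological deficit with at least one of the following: change in level of consciousness", followed by further signs.
- **Stroke rather than TIA:** "Duration of a focal or global neurological deficit ≥24 hours; OR <24 hours, if available neuroimaging documents a new hemorrhage or infarct", or a deficit that results in death.
- **Ischemic class:** "An acute episode of focal cerebral, spinal, or retinal dysfunction caused by infarction of central nervous system tissue".
- **Hemorrhagic class:** "An acute episode of focal or global cerebral or spinal dysfunction caused by intraparenchymal, intraventricular, or subarachnoid hemorrhage".
- **Closing rule:** "Patients with non-focal global encephalopathy will not be reported as a stroke without unequivocal evidence of cerebral infarction based upon neuroimaging studies", with CT and brain MRI given as the imaging methods.

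Encephalopathy is not defined. The SAP lists stroke among its endpoints (Sections 3.4, 3.5, 3.7 and 3.10) but does not define it. The opening of Appendix B refers further detail to the CEC Charter and adds: "In case of inconsistency between the protocol and the CEC Charter, the CEC Charter will be the final determining document". The Charter is not among the documents.

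Stroke enters these endpoints:

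- the primary safety endpoint (Protocol Section 5.2): "Overall rate of device and procedure related Major Adverse Events (MAEs) through 30 days post-procedure (including death, stroke, myocardial infarction", with further components;
- the 30-day secondary safety endpoints (Section 5.3);
- Clinical Success, through its MAE condition (Section 5.5);
- 1-year Patient success (Section 5.5): "Patient remains alive and stroke free, and";
- the long-term safety outcomes through 1 year (Section 5.8).

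**The concern.** Three of the five clauses (entry, stroke versus TIA, hemorrhagic class) admit a global deficit caused by hemorrhage. The closing rule makes one exception for imaging-proven disease, and that exception covers infarction only. For one kind of patient, the definition therefore gives adjudicators two opposite answers.

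At stake is whether the reported stroke and MAE rates count every imaging-proven stroke. Safety is summarised as event rates with confidence intervals, so completeness of the count is what gives those rates their meaning. The 30-day safety endpoints cover the Device group only, so an omitted event can only lower the rate reported there.

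**Working it through.** The plan states no stroke rate and no safety performance goal, so there is no figure to reproduce. The main check is to take one hypothetical patient through the clauses.

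**Patient:** reduced consciousness for more than 24 hours, no focal sign, CT-proven subarachnoid hemorrhage, no infarct, and a clinical label of non-focal global encephalopathy.

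| Clause | What it asks | Result |
|---|---|---|
| Entry | Focal or global deficit with a listed sign; change in consciousness is listed | Met |
| Stroke vs TIA | Focal or global deficit of at least 24 hours, or shorter with new hemorrhage or infarct on imaging | Stroke |
| TIA | Under 24 hours and no new hemorrhage or infarct on imaging | Not met |
| Hemorrhagic class | Focal or global dysfunction caused by hemorrhage | Met |
| Closing rule | Unequivocal infarction on imaging | Not met, so not reported as a stroke |

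The closing rule reverses the result of the others. The event cannot fall back to TIA either, because the imaging shows hemorrhage.

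**Other routes into the MAE composite.** Appendix B places intracranial bleeding under life-threatening bleeding, but the MAE components in Protocol Section 5.2 and SAP Section 3.4 do not include bleeding as such. A fatal case can enter as a death if it is device or procedure related. A non-fatal case has no route through bleeding.

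**Scale of one event.** Inputs: 375 mITT patients (Protocol Section 13.3.3) and 2:1 allocation (Section 7). Device group ≈ 375 × 2/3 = 250. One omitted event changes the rate by 1/250 = 0.4 percentage points. Exact (Clopper-Pearson) 95% intervals for small counts in 250:

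| Strokes | Rate | 95% CI |
|---|---|---|
| 0 | 0% | 0 to 1.46% |
| 1 | 0.4% | 0.01 to 2.21% |
| 2 | 0.8% | 0.10 to 2.86% |
| 3 | 1.2% | 0.25 to 3.47% |

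**How many events.** This needs three inputs that the documents do not give. As assumptions only, take a stroke rate of 2 to 4%, a hemorrhagic share of 10 to 25%, and a non-focal share of those of 20 to 50%. Expected omitted events = 250 × stroke rate × hemorrhagic share × non-focal share.

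- Low: 250 × 0.02 × 0.10 × 0.20 = 0.1
- High: 250 × 0.04 × 0.25 × 0.50 = 1.25

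The upper end is too high for this purpose, because the rule covers encephalopathy, which is narrower than every non-focal presentation. About 0 to 1 event is a fair reading.

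**The case against.** **The rule is narrow.** It bars non-focal global encephalopathy, not every non-focal event. An adjudicator faced with a proven subarachnoid hemorrhage could apply the hemorrhagic definition directly and never use the encephalopathy label. This stands: omission is possible, not certain. It does not remove the conflict, because encephalopathy is undefined and a change in consciousness is itself a qualifying stroke sign.

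**The Charter may already settle it.** It prevails over the protocol, and Protocol Section 14.2 requires it to hold consistent definitions. This also stands, but it cannot be checked here, and the protocol text still contradicts itself.

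**The event would be recorded elsewhere.** Adverse events go on the eCRF (Protocol Section 11.5.1), and site-reported and adjudicated events are tabulated (SAP Section 9.2). That is correct. The gap is in the stroke and MAE counts, not in event reporting.

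**The endpoints are descriptive.** The safety endpoints are rates with 95% confidence intervals (Protocol Section 13.4.3, SAP Section 8.3). Patient success and the long-term safety outcomes are summarised descriptively (SAP Sections 8.5 and 8.8). Patient success changes only if the affected patient is also alive, free of heart failure re-hospitalization and improved on two of three measures. All of this stands and limits the consequence.

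**What a reader might infer beyond this.** Because the protocol recommends antithrombotic therapy around the implant, a reader might conclude that the rule biases the comparison between arms towards the device. The documents do not support that. The rule applies equally to both arms, the 30-day endpoints have no comparator, and no stroke rate by arm or type is given. A reader might also want the ischemic class widened, since the closing rule admits a global event with infarction while that class is focal only. This affects the subtype label alone, and no listed endpoint uses stroke subtype.

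**Conclusion.** The conflict is certain on the face of Appendix B, and nothing in the SAP resolves it. Its effect is limited: a patient labelled with non-focal global encephalopathy who has imaging-proven intracranial hemorrhage and no infarct could be left out of the stroke count and, if the event is not fatal, out of the MAE composite.

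The likely number is about 0 to 1 in roughly 250 Device patients, on the assumed rates shown. Each such event lowers the observed rate by about 0.4 percentage points, which is small beside the width of the intervals above. No alpha, power or hypothesis test changes. The conclusion assumes that the Charter does not already correct the wording. It does not extend to every non-focal hemorrhage, nor to a claim of bias between the arms. It is worth correcting because stroke is a primary safety component and the correction costs almost nothing.

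**What to change.** In the closing rule of Appendix B, insert *or intracranial hemorrhage* directly after the reference to cerebral infarction, so that either finding on neuroimaging allows the event to be reported as a stroke. Confirm that the CEC Charter carries the same wording, since it decides in case of conflict, and do so before events are adjudicated. If any have been adjudicated already, recheck those set aside as encephalopathy for hemorrhage on imaging.

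Aligning the ischemic class with the closing rule is optional tidying and not needed for any endpoint.

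The cost is a few words in the protocol and, if needed, the Charter. No new data, visits or analyses are required.

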APPENDIX C: ECONOMIC DATA COLLECTION CORE LAB

An independent core laboratory will be used for the collection of hospital billing data for patients randomized to treatment with the Cardioband device, and for the conduct of a detailed health economic analysis that will include analysis of data collected during the trial, as well as projection of long-term outcomes in a disease simulation model. This study component aims to collect bills, along with other data, to evaluate the economic value of the Cardioband ACTIVE trial intervention arm versus control group. Under no circumstances will billing data from any single patient or institution be identified or shared with any outside party.

Economic Data Collection

The ACTIVE trial will include a prospectively planned health economic study component designed to assess the potential health economic value of the Cardioband intervention arm versus the control arm. Throughout this trial, Baim Institute will be acting on behalf of Edwards to obtain and analyze copies of subject hospital bills for patients treated with the Cardioband system (roll-ins and patients randomized to Cardioband). Specifically, Baim Institute will be seeking a UB-04 Summary bill and an Itemized Bill for each initial hospitalization. Bills will not be collected for patients randomized to the control group, since they are not automatically hospitalized.

Detailed resource utilization data, including information on all hospitalizations and residential care services will be collected on all study patients. In addition, patients randomized to the Cardioband procedure who are willing to participate in the economic study will provide separate, written consent for the collection of hospital billing data for the admission during which the Cardioband procedure is performed.

"In-trial" health care costs will be calculated for all study patients using a combination of resource-based and cost-accounting methods. The cost of index hospitalizations for Cardioband procedures will primarily be derived from the collected hospital billing data. The costs of follow-up hospitalizations will be estimated on the basis of measured data regarding those admissions, and national reimbursement for similar clinical events. If there are important differences in medical therapy observed between the groups during the trial, these may be considered, if the clinical data allow. A long-term health economic model comparing the cost-effectiveness of Cardioband to medical therapy in the study population will then be constructed. The preferred horizon for the model will be lifetime.

PROTOCOL NUMBER: 2017-05

The long-term health economic model will combine empirical data on costs, survival and quality of life from the initial 12-month in-trial period, combined with long-term projections of those same parameters. Projections of survival will be uncertain given the size and duration of the study and varied survival functions and assumptions will need to be explored in scenario and sensitivity analysis. Projections of long-term quality of life and health care costs will be derived from in-trial data, where possible, supplemented with estimates from external literature (e.g. from patients with functional mitral regurgitation treated in other trials) as needed. Plausible ranges for all important model parameters will be estimated and the impact of variation in those parameters will be assessed with appropriate sensitivity analyses.

Billing Data Collection

Bills will need to be collected from your hospital billing department, and sent to the EQOL Group at the Baim Institute. A separate Medical Billing Release (MBR) Form from Baim Institute will be provided along with the site's Informed Consent Form. We request the Study Coordinators fax or email a copy of the MBR form to the Baim Institute team and mail the original MBR form to Baim Institute.

Sites will scan & email or fax bills using the information listed below. The MBR form and bills will arrive at Baim Institute through a secure system used for the transmission of source documents for many clinical trials. All billing data will be completely de-identified by the EQOL Group at Baim Institute immediately upon receipt. This billing information will be handled in a strictly confidential manner and used only for research purposes. No hospital name or subject identifiers will be disclosed or used in any format in reports or publications generated with these data.

PROTOCOL NUMBER: 2017-05

### 1. INTRODUCTION

This statistical analysis plan (SAP) specifies the statistical methods to be implemented for the analysis of data collected within the scope of Edwards Lifesciences's Protocol ACTIVE 2017-05 and provides detailed instructions as to how each analysis will be performed.

### 2. STUDY DESIGN

### 2.1 Study Objective

The objective of this study is to evaluate the efficacy and safety of transcatheter mitral annular reduction for functional mitral regurgitation (MR) plus guideline directed medical therapy (GDMT) compared to GDMT alone.

#### 2.2 **Overall Study Design and Plan**

This study is a prospective, randomized, multicenter clinical evaluation of the Edwards Cardioband System for the treatment of clinically significant functional mitral regurgitation in MR patients who are treated in accordance with current ACC/AHA valve guidelines. The study design incorporates a roll-in cohort to provide experience in use of the Edwards Cardioband System prior to randomizing patients into the pivotal study cohort at a given investigational site. The roll-in cohort will include a maximum of three patients per site (e.g. if 75 sites used, a maximum of 225 roll-in patients). Data for the roll-in patients will be presented and analyzed as a separate cohort. All patients are followed for 30 days, 6 months, 1 year, and annually for a total of five years post-index procedure or randomization in the case of the Control population.

#### 2.3 Randomization and Blinding

Randomization is ideally performed within seven days prior to the scheduled procedure, but no more than 14 days prior. If a patient is randomized to Control, the scheduled interventional case is cancelled and the patient is notified that they have been enrolled in the Control/medical therapy arm of the trial and will not need to undergo an interventional procedure. The process of randomizing after a case is scheduled has been implemented to ensure that the time frame between randomization and actual treatment is minimized. Eligible patients will be randomly assigned in a 2:1 ratio to either Device group or Control group, respectively.

Randomization schedule will be generated using the Balance module in Medidata RAVE, the Electronic Data Capture System for the study. Randomization will be stratified by (a) site and (b) baseline ischemic vs non-ischemic disease. This randomization schedule will be masked to patients, site personnel, study team, and sponsor as defined in the Randomization and Blinding Plan. Only the unblinded statistician and designates will be privy to the masked randomization scheme.

All analyses of data by the study statistician/programmer will be conducted blinded to treatment assignment (similar to the conduct of blinded clinical study to the extent possible), until the time of database lock for the primary endpoint analysis. Analyses of unblinded data such as DSMB analysis will be performed by a separate non-study or independent statistician/SAS programmer.

